3.7. Schedule of Events

Please see the protocol Tables 2-1, 2-2 for a detailed schedule of events.

4. Statistical Analysis and Reporting

All efficacy and safety statistical analysis will be based on data from stages 1, 2, 3 and 4 combined, unless specified otherwise.

[figure not shown]

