6.1 NRS Pain

For all outputs the placebo group will include subjects pooled across stages 2 and 3.

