3.1. Overall Design

3.2. Sample Size and Power

There will be 4 stages in the study: in the first stage, subjects will be randomly assigned to placebo or the lowest dose (CCI) until at least 10 subjects have been recruited. In the second stage, up to 30 subjects will be randomly assigned to a placebo or CCI of MEDI7352; prior to commencing the third stage, the safety and tolerability experience following administration of multiple doses of CCI in the Phase 1 study of MEDI7352 will be evaluated. In stage 3 of the study, approximately 67 subjects will be randomly assigned to placebo or CCI of MEDI7352. The third stage will include an interim analysis to enable decision making for stage 4 with respect to the sample size and dose allocation ratio. If no changes are made following the interim analysis, in stage 4 of the study, approximately 165 eligible subjects will be randomly assigned to treatment across 3 dose levels of MEDI7352 (CCI) or placebo, to ensure that approximately 236 subjects are evaluable for the efficacy analysis of stages 2 to 4 combined. The number of subjects in the fourth stage is currently planned to follow an equal treatment allocation to each of the 4 treatment groups. However, the exact number of subjects and the allocation to each dose in stage 4 will be determined after the interim analysis.

There is no formal sample size calculation for stage 1; 10 subjects in stage 1 are considered sufficient for the initial assessment of safety. The sample size for stages 2-4 combined was determined by a formal power calculation (see below) and the size of stage 3 was defined to enable decision making for the stage 4 sample size and dose allocation ratio.

This study is powered at greater than 80% to detect a statistically significant (1-sided alpha = 0.025) dose-response relationship when the true Week 12 placebo-corrected change from baseline difference at the $\boxed{\text{CCI}}$ dose is 1.25 on the 11-point NRS scale (MEDI7352-placebo treatment) and the true dose-response follows a hyperbolic Emax relationship, with ED50 within the range 1-750 µg/kg. This calculation also assumes:

- The true standard deviation (SD) is 2.4, which is based on other studies undertaken with pregabalin in PDN (Satoh et al. 2011, Lesser et al. 2004, Rosenstock et al. 2004, Tölle et al. 2008).

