- The data from stages 2, 3, and 4 are combined so that the number of subjects for the dose-response analysis is 236 with the total number evaluable for placebo, column doses equal to 81, 37, 51, and 67, respectively. This is comprised of, assuming an overall 10% non-evaluability rate:
 - o 28 out of 30 randomised in stage 2; 14 per arm
 - o 60 out of 67 randomised in stage 3; 30 per arm, and
 - o 148 out of 165 randomised in stage 4; 37 per arm
- The dose-response hypothesis test is multiplicity adjusted as described by Pinheiro et al. 2006 in order to control the type 1-error.

The above calculations were performed using the software R and the R-package 'DoseFinding' [https://cran.r-project.org/web/packages/DoseFinding/DoseFinding.pdf] with the following parameters:

- Population SD (of change from baseline to week 12) = 2.4
- Placebo effect = 1 point reduction in NRS and CCl effect = 2.25 reduction from baseline, ie, delta= 1.25
- Linear contrasts were determined from 5 'candidate dose' response models which are all E_{max} models with decreasing potency/increasing ED50: 7.5, 15, 30, 60, 750 μg/kg. The 5th case is essentially linear in dose. E_{max} models were chosen following the recommendations in a recent meta-analysis of dose response studies by Thomas et al., 2014.
- Power was assessed across 16 alternative true dose response curves, 12 E_{max} with ED50 ranging from 0.375 to 750 μg/kg, 3 logistic and 1 quadratic, all having a Week 12 placebo-corrected change from baseline difference at the column dose of 1.25.

[figure not shown]
The overall withdrawal rate is anticipated to be approximately 10%. However, since the primary analysis will use Last Observation Carried Forward (LOCF) for withdrawn subjects, and the SD estimate is taken from studies which also used the LOCF approach, the only additional subjects recruited will be to account for withdrawals in stages 2, 3, and 4 if withdrawal occurs at, or prior to, the Week 2 visit.

The number of subjects who will agree to participate in the genetic research is unknown. It is therefore not possible to establish whether sufficient data will be collected to allow a formal statistical evaluation or whether only descriptive statistics will be generated.

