3.5. Method of Assigning Subjects to Treatment Groups

The randomisation schedule will be computer generated using a permuted block algorithm appropriate to the treatment groups included in each stage and will randomly allocate investigational product (IP) to randomisation numbers. The randomisation numbers will be assigned sequentially through a central interactive web response system (IWRS) as subjects are entered into the study. The randomisation schedule will not be stratified, and study centre will not be a blocking factor in the randomisation schedule.

[figure not shown]
The randomisation schedule has been prepared by Premier Research before the start of the study. No one involved in the study performance will have access to the randomisation schedule before official unblinding of treatment assignment. No subject will be randomised into this study more than once.

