8.1. Primary Efficacy Analysis

The primary efficacy endpoint of this study is the change in the weekly average of the average daily pain scores from the baseline week to Week 12 measured on an 11-point (0-10) NRS.

MCP-Mod approach. The main statistical analysis of the primary efficacy endpoint will use the MCP-Mod approach on LOCF data, which is a well-established statistical methodology for establishing both the existence of a dose response and modelling the underlying dose-response relationship. The modelling step ('MOD' step) from the MCP-MOD approach will only be conducted if stage 4 is initiated, otherwise there would be insufficient dosing data to fit the non-linear models.

There are two steps to MCP-Mod:

AD-ST-33.06 Effective date: 12-Nov-2020

- 1. The 'MCP' step is a rigorous method to establish presence of a dose response while protecting the type I error and, if the dose-response relationship is statistically significant, then
- 2. The 'MOD' step estimates the dose response function and associated model parameters.

The MCP test will use linear contrasts corresponding to the five candidate models described in Section 3.2. The test will use pre-specified model parameters and optimal contrasts for each will be generated. The hypotheses are as follows:

Null hypothesis (H₀): Optimal contrasts $\mu \ge 0$ for all models

Alternative hypothesis (H_A): Optimal contrasts μ <0 for at least one model

where μ is the true event rate.

The underlying model will be an ANCOVA with dependent variable 'change from baseline to Week 12 (LOCF)', and independent variables will include:

- dose group as a factor variable with the placebo group as the reference level
- baseline score, i.e. baseline weekly average pain (NRS), as a continuous variable
- co-medication type.

The random error is assumed to be normally and independently distributed with constant variance. The parameter estimates of the difference between each dose group and placebo, least square (LS) Means estimates of change from baseline to Week 12 for each dose, standard errors, 95% unadjusted, 'Lalonde-type' asymmetric CI (i.e., lower limit of 1-sided 90% CI and upper limit of 1-sided 80% CI), and *P* values will be presented.

[figure not shown]

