'MOD' step [3] Selected Model xxxxxxxxx

Parameter	Estimate	95% CI of Estimate [6]
ED50	XX.X	[x.xx to x.xx]
ED90 [4]	XX.X	[x.xx to x.xx]
Asymptotic ED90 [5]	XX.X	[x.xx to x.xx]
Dose to achieve target (-1.25) effect	XX.X	[x.xx to x.xx]
Treatment effect at dose = 5 mcg	XX.X	[x.xx to x.xx]
Treatment effect at dose = 50 mcg	XX.X	[x.xx to x.xx]
Treatment effect at dose = 150 mcg	XX.X	[x.xx to x.xx]
Treatment effect at dose = 450 mcg	xx.x	[x.xx to x.xx]

CI: Confidence Interval; LOCF = Last Observation Carried Forward; MCP = Multiple Comparisons; Procedure; MOD = Modelling; NRS = Numeric rating scale.

Programming Notes:

• The 'MOD' step will only be performed if stage 4 is initiated, otherwise there would be insufficient dosing data to fit the non-linear models.

Final 1.0 | 12-Jul-2023 | Page 27 of 205

^[3] Results from the 'MOD' step will only be available in case any of the MCP tests is statistically significant.

^[4] ED90 = Effective Dose giving 90% of the effect of the maximum dose studied.

^[5] Asymptotic ED90 = Effective Dose giving 90% of the asymptotic maximum effect.

^{[6] 2.5%} and 97.5% quantiles taken from 100000 samples from the multivariate normal distribution for model fitted estimates and its covariance matrix. Reference Listing: 16.2.6.1

[figure not shown]

Table 14.2.1.2.2 Statistical Analysis of CFB to Week 12 Daily Pain NRS: Primary ANCOVA Analysis (LOCF) mITT Population

Model parameter estimates

					2-sided 95% unadjusted Asymmetric CL		2-sided
Parameter	Estimate	t value	Degrees of freedom	Standard Error	CL	[1]	P-value [2]
Intercept	XX.XX	XX.XX	•	xx.xxx	[x.xx to x.xx]		
Co-Medication Type			2				0.xxxx
Baseline pain NRS	XX.XX	XX.XX	1	XX.XXX	[x.xx to x.xx]		0.xxxx
Active 5 mcg vs Placebo	XX.XX	XX.XX	1	XX.XXX	[x.xx to x.xx]	[x.xx to x.xx]	0.xxxx
Active 150 mcg vs Placebo	XX.XX	XX.XX	1	XX.XXX	[x.xx to x.xx]	[x.xx to x.xx]	0.xxxx
Active 450 mcg vs Placebo	XX.XX	XX.XX	1	XX.XXX	[x.xx to x.xx]	[x.xx to x.xx]	0.xxxx
Model residual standard deviation	XX.XX						

ANCOVA = analysis of covariance; CFB = Change from Baseline;

CL = Confidence limits; LOCF = Last Observation Carried Forward; NRS = Numeric rating scale.

[2] P-value is derived from the following model: ANCOVA by dose using NRS baseline value and co-medication as covariates, with CFB to Week 12 (LOCF) as dependent variable.

Least Square Means

Treatment	Number of Subjects	LS mean [3]	95% CI of LS mean
Active 450 mcg	XX	X.XX	[x.xx to x.xx]
Active 150 mcg	XX	X.XX	[x.xx to x.xx]

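### Stages with different arms and separate randomisation are pooled without a stage term, so the 0.025 error rate of the primary dose-response test is assured only if nothing drifts between stages

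*SAP*

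**What the plan says.** Section 3.5 describes a "permuted block algorithm appropriate to the treatment groups included in each stage", so subjects were randomised within stage. Section 3.2 sets out the arms. Stage 1 is placebo or the lowest dose, stages 2 and 3 are each placebo or a single dose, and stage 4 is placebo plus three doses in equal allocation.

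Section 4 then sets the default that "All efficacy and safety statistical analysis will be based on data from stages 1, 2, 3 and 4 combined, unless specified otherwise". The primary model in Section 8.1 contains "dose group as a factor variable with the placebo group as the reference level", baseline weekly average pain and co-medication type. The MMRM adds time and treatment by time. Neither has a stage term. Section 10 removes the supplementary analysis that would have analysed stages 2+3 and stage 4 separately and combined the p-values.

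The sample size is built on a narrower set: "The data from stages 2, 3, and 4 are combined so that the number of subjects for the dose-response analysis is 236" (Section 3.2). Section 8.1 does not repeat that restriction. The v1.0 shell for the primary ANCOVA (Table 14.2.1.2.2) has a row "Active 5 mcg vs Placebo".

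The interim plan (SiAP) works the same way. Section 6.1 says "For all outputs the placebo group will include subjects pooled across stages 2 and 3", the ANCOVA in Section 6.1.5 adjusts for baseline only, and the conditional-power simulation in Appendix A2 passes baseline as its only covariate.

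**The concern.** Randomisation balances the arms within a stage, not across stages. The dose groups draw on different stages, so a pooled placebo group contains subjects recruited when a given dose was not on offer. If placebo response, site mix or study conduct changes between stages, part of that change enters the dose-placebo differences. It can look like a dose response or hide one.

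Section 8.1 says the MCP step protects the type I error. Without a stage term that also requires the stage means to be equal, which the SAP neither states nor checks. With the stage-wise analysis removed, no planned output would reveal a shift.

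The analysis set adds to this. If the Section 4 default is applied to the primary test, stage 1 enters as well. Its dose would be compared almost entirely with placebo subjects from other stages.

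**Working it through.** **Inputs.** From Section 3.2: SD 2.4, one-sided alpha 0.025, five Emax candidates (ED50 7.5, 15, 30, 60, 750 µg/kg), and a top-dose effect of 1.25 ("2.25 reduction from baseline, ie, delta= 1.25"). Evaluable subjects per arm are 14 in each of two arms (stage 2), 30 in each of two (stage 3) and 37 in each of four (stage 4). The doses are redacted in Section 3.2. I took 50, 150 and 450 from the shells (Table 14.2.1.2.1). Drift sizes are my assumptions, since the document gives none. Baseline and co-medication are left out, so 2.4 serves as the residual SD.

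**The plan's counts reproduce.** Placebo 14 + 30 + 37 = 81; stage-4-only dose 37; stage 2 dose 14 + 37 = 51; stage 3 dose 30 + 37 = 67; total 236.

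**The plan's power reproduces.** Section 3.2 says "This study is powered at greater than 80% to detect a statistically significant (1-sided alpha = 0.025) dose-response relationship". The five-contrast test with a multivariate-t critical value gives 94.8% at ED50 1, 91.9% at 30 and 87.5% at 750.

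**Non-concurrent share of placebo:**

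| Dose group | Stages 2-4 | Stages 2-3 only |
|---|---|---|
| stage 4 only (n = 37) | 44/81 = 54% | not given |
| stages 2 and 4 (n = 51) | 30/81 = 37% | 30/44 = 68% |
| stages 3 and 4 (n = 67) | 14/81 = 17% | 14/44 = 32% |

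If stage 1 is pooled (10 subjects, split not stated, assumed 5:5), the share for its dose is 81/86 = 94%, or 92-96% with 3 to 7 on active.

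**Bias.** For a shift s in stage 4, bias = s × (stage 4 fraction of the dose group − stage 4 fraction of placebo). With s = 0.5:
- n = 37: 0.5 × (37/37 − 37/81) = 0.27
- n = 51: 0.5 × (37/51 − 37/81) = 0.13
- n = 67: 0.5 × (37/67 − 37/81) = 0.05

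Without stage 4, a 0.5 shift in stage 3 gives −0.5 × 30/44 = −0.34 for the stage 2 dose and 0.5 × (1 − 30/44) = +0.16 for the stage 3 dose.

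**Rejection rate under the null (nominal 0.025; + means more improvement):**

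| Scenario | No stage term | Stage factor |
|---|---|---|
| Stages 2-4, stage 4 +0.5 | 0.041 | 0.025 |
| Stages 2-4, stage 4 −0.5 | 0.019 | 0.025 |
| Stages 2-3 only, stage 3 +0.5 | 0.037 | 0.025 |
| Stages 2-3 only, stage 3 −0.5 | about 0.020 | 0.025 |

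**Cost with stage 4.** SEs of the dose-placebo differences go from 0.476, 0.429 and 0.396 to 0.513, 0.455 and 0.406, a rise of 8%, 6% and 3%. Power becomes 93.7%, 91.3% and 86.5% at ED50 1, 30 and 750.

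**Cost without stage 4.**
- Stage 2 dose: 2.4 × √(1/14 + 1/44) = 0.736 becomes 2.4 × √(2/14) = 0.907, +23%.
- Stage 3 dose: 2.4 × √(1/30 + 1/44) = 0.568 becomes 2.4 × √(2/30) = 0.620, +9%.
- Power of the dose-response test is below 80% with or without the factor. It moves from 65% to 66% at ED50 1 and from 57% to 54% at ED50 750.

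**The case against.** The strongest defence is that the pooling is pre-specified, the study is double-blind with placebo in every stage, and stage 4 randomises all four arms concurrently and supplies 148 of the 236 subjects. Under the full design the top-dose contrast is well protected: a whole 1-point shift in stage 4 biases it by about 0.10, against a target of 1.25. All of this stands, and it limits the size of the problem.

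Three stronger readings are tempting, and the documents do not support them.

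- A reader might infer that the dose effects rest largely on non-concurrent placebo. Under the planned design that is true only of the stage-4-only dose (54%). The other two have 37% and 17%.
- A reader might infer that type I error control fails. It is not assured, which is weaker. No drift is documented, and its direction matters: worsening in stage 4 makes the test conservative. A 0.5 shift confined to stage 3 moves the rate little in either direction (0.027 or 0.031). Rates near 0.045 and 0.08 need no stage 4, stage 1 included, and a stage 3 improvement of 0.5 or 1.0 points, all at once.
- A reader might infer from the 5 mcg row that stage 1 definitely enters the primary test. That row is in the v1.0 shells, and the v1.1 shells as supplied stop before the efficacy tables. Section 4 also allows exceptions, and Section 3.2 can be read as one. What remains is an ambiguity in Section 8.1.

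Nor is the interim itself a type I error problem. The SiAP plans estimates, intervals, posterior probabilities and conditional power, and no MCP test on the interim data alone. The same bias does carry into those estimates.

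**Conclusion.** The point holds in this form: the primary analysis leaves out the factor within which subjects were randomised, so its error rate and dose estimates are protected only if stage means do not differ. For an assumed half-point shift in stage 4, the one-sided 0.025 becomes about 0.041 or about 0.019 depending on sign, with bias of up to 0.27 points for the stage-4-only dose and 0.05 for the top dose. If stage 4 is not run, the same shift in stage 3 biases the stage 2 dose by 0.34 points.

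These sizes rest on SD 2.4, the shell doses and drift values that I chose. The stage factor removes the bias exactly when a shift is additive, that is, common to all arms in a stage. It would not remove a treatment effect that itself changes between stages.

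**What to change.** 1. Add stage as a fixed factor to the primary ANCOVA and MCP contrasts, the MOD fit and the MMRM (SAP Section 8.1, with the covariate list in Section 6.1.2).
2. Make the same change in the SiAP ANCOVA (Section 6.1.5) and in the covariates of the conditional-power code (Appendix A2).
3. State in Section 8.1 that the primary dose-response test uses stages 2-4, as sized in Section 3.2, so that the Section 4 default does not bring stage 1 in. Align the ANCOVA and MOD shells with that statement.
4. Show the pooled result without the stage term as a sensitivity analysis. This matters most if stage 4 is not run.

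The cost is wording and a covariate in the code, with the precision loss set out above: 3-8% on the SE with stage 4, and 23% and 9% for the stage 2 and stage 3 doses without it. A stage stratum in the CMH tests is not needed. It would multiply the four existing strata by three for a secondary analysis, with only 28 evaluable subjects in stage 2.

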4.1. Introduction

Data processing, tabulation of descriptive statistics, calculation of inferential statistics, and graphical representations will primarily use SAS (release 9.4 or higher). The multiple comparison and modelling (MCP-Mod) analysis will be performed using R (release 4.2.1 or higher) and the DoseFinding package (version 1.0-3 or higher). If a use of other software is warranted, the final statistical methodology report will detail what software was used for what purposes.

Continuous (quantitative) variable summaries will include the number of subjects (n) with non-missing values, the number of missing values, arithmetic mean, SD, median, 1st, and 3rd quartiles (where applicable), minimum, and maximum.

Categorical (qualitative) variable summaries will include the frequency and percentage of subjects who are in the particular category or each possible value. In general, the denominator for the percentage calculation will be based upon the total number of subjects in the study population for the treatment group, unless otherwise specified. The denominator for by-visit displays will be the number of subjects in the relevant study population with non-missing data at each visit, unless otherwise specified.

The minimum and maximum will be reported with the same degree of precision (i.e., the same number of decimal places) as the observed data. Measures of location (mean and median) will be

reported to 1 degree of precision more than the observed data and measures of spread will be reported to 2 degrees of precision more than the observed data.

For derived data, minimum and maximum will be reported to 2 degrees of precision. Measures of location (mean and median) will be reported to 3 degree of precision, and measures of spread will be reported to 4 degrees of precision.

Percentages will be presented to 1 decimal place, unless otherwise specified.

Unless otherwise indicated, all statistical tests will be conducted at the 0.025 significance level using 1-tailed tests, and *P* values will be reported. For estimation purposes, 2-sided 95% confidence intervals (CI) will be presented.

Total NGF and PK concentration data will be summarized by dose as per the quantitative variables and presenting the number (n) of non-missing observations, and the n < lower limit of quantification (LLOQ). PD and PK parameters will be summarized by dose and will include the arithmetic mean, SD, geometric mean (gmean), gmean \pm geometric SD, geometric coefficient of variation (gCV%), median, minimum and maximum.

4.2. Interim Analysis and Data Monitoring

Details of the interim analysis have been included in the Statistical Interim Analysis Plan (SiAP) version 1.0 dated 10-Feb-2023.

[figure not shown]
5. Analysis Populations

The following analysis populations are planned for this study:

- Screening Population (Screened): All subjects who provide informed consent and/or assent and provide demographic and/or baseline screening assessments, regardless of the subject's randomisation and treatment status in the study. The Screening Set will be analysed as randomised, according to planned treatment.
- Safety Population (SAF): The Safety Population includes all subjects who receive at least 1 dose of double-blind study medication. The Safety Set will be analysed according to actual treatment.
- Modified Intent-To-Treat Population (mITT): The modified intent-to-treat population will be used for all efficacy analyses and will include all randomised subjects who receive at least 1 dose of double-blind study medication and have at least 1 daily NRS assessment while receiving double-blind treatment. The mITT Set will be analysed as randomised, according to planned treatment.
- Pharmacokinetic Population (PK): The PK Population will include all subjects for who a PK sample was obtained and analysed. The PK Set will be analysed according to actual treatment.

Assignment of subjects to populations will be confirmed at a blinded data review meeting to be

AD-ST-33.06 Effective date: 12-Nov-2020

held before the study database is locked.

If a subject is randomised incorrectly or is administered the incorrect IP, analyses of the mITT population will be based on the IWRS-assigned treatment whereas all other analyses will be based on the actual treatment.

6. General Issues for Statistical Analysis

6.1. Statistical Definitions and Algorithms

6.1.1. Baseline

For all safety endpoints, the last observation recorded prior to the first dose of treatment will be used as the baseline observation for calculations of change from baseline.

For pain diary data the baseline period is defined as the seven-day period prior to randomization, i.e., Day -7 to Day -1, inclusive. A subject is considered to have an evaluable baseline pain score if there are at least 4 days of recorded diary pain scores in the 7-day period.

